### 4.1 Sample Size and Controlling for Multiplicity

#### 4.1.1 Sample Size - Primary Endpoint

The primary safety and efficacy endpoint of the trial is target lesion failure (TLF), defined as the per-subject hierarchical composite of cardiac death, target vessel-related myocardial infarction (TV-MI), and clinically-driven target lesion revascularization (TLR), evaluated at 12 months.

We assume:

- Randomization ratio is 2:1 (BuMA DES: DP EES)
- The true rate of TLF in the Control group at 12 months = 6.5%
- No difference between treatments (the true rate of TLF in the Intervention group at 12 months = 6.5%)
- Non-inferiority margin ( $\Delta$ ) = 3.575%
- Loss to follow-up at 1 year (inclusive of dropout from co-primary PP analysis population) = 5% (a standard assumption for contemporary trials of coronary stents)
- $\alpha$  = 0.025 (one-sided)

Given these assumptions, a sample size of 1551 evaluable subjects (1034 Intervention: 517 Control) will provide 80% power to demonstrate non-inferiority of the BuMA DES to DP EES using the Farrington-Manning approach. The sample size has been increased to 1632 subjects (1088 Intervention: 544 Control) to account for an expected 5% loss to follow-up at 12 months.

The expected event rate of the primary endpoint (target lesion failure [TLF] at 12 months) in the Control group was estimated based on published data from randomized controlled trials of commercially-available durable polymer everolimus-eluting coronary stent systems (DP EES). Based on published literature reporting TLF at 1 year in subjects treated with DP EES, the expected event rate for the primary efficacy endpoint in the control group is estimated to be 6.5%. Details and rationale for assumption with regards to the expected control event rate are provided in Protocol Section 11.3.3.1.

	FORM	Document No BIO-TMP-0702 Revision: 00
	TITLE Statistical Analysis Plan	Effective date: 16-Mar-2018 Department: BIO

A meta-analysis of historical trials determined that a conservative estimate (lower bound of the 90% CI) for the treatment effect of the Control comparator (DP EES) compared to bare metal stents (BMS) was 9.0% for the primary endpoint of TLF at 1 year. The selected non-inferiority margin of 3.575% therefore preserves >60% of the risk reduction provided by the Control using the fixed margin approach. This clinical margin is more conservative than the usual practice in cardiovascular outcomes studies of selecting a non-inferiority margin that preserves 50% of the Control effect size.

#### 4.1.2 Sample Size - Secondary Powered Endpoint

The powered secondary endpoint of the trial is long-term safety and efficacy, defined as TLF between 12 months and 5 years by landmark analysis. The analysis will be performed when the last enrolled subject has completed his/her 5 year clinical follow-up visit.

We assume:

- Randomization ratio is 2:1 (BuMA DES: DP EES)
- The landmark (between 12 months and 5 years) TLF rate in the Control group = 8%
- The rate of TLF in the control group at 12 months = 6.5%
- A constant Hazard Ratio in the Intervention group compared to the Control Group = 0.52
- Loss to follow-up = 5% per year (a standard assumption for contemporary trials of coronary stents)
- $\alpha = 0.05$  (two-sided)

Given these assumptions, the planned study sample size of 1444 evaluable subjects at 1 year (accounting for an estimated 5% loss to follow-up at 1 year, a 6.5% rate of TLF prior to 1 year, and a continued annual loss to follow-up of 5%) will provide approximately 80% power to demonstrate superiority of the BuMA DES to DP EES using the log-rank test.

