### 1.2.1 Trial Hypotheses

#### 1.2.1.1 Primary Safety and Efficacy Hypothesis

The primary hypothesis is that the rate of TLF in the Intervention group is non-inferior to the rate of TLF in the Control group by greater than or equal to the pre-specified non-inferiority margin ( $\Delta$ ). Specifically, the null and alternative hypotheses are:

$$H_0: p_I - p_C \geq \Delta$$

$$H_A: p_I - p_C < \Delta$$

Where:

$p_I$  = the true rate of TLF in the Intervention group at 12 months

$p_C$  = the true rate of TLF in the Control group at 12 months

$\Delta$  = non-inferiority margin

The non-inferiority criterion is met if the upper bound of the 95% confidence interval (97.5% one-sided confidence interval) of the difference between the Intervention and Control group event rates is less than the specified delta, using the Farrington-Manning approach.

	FORM	Document No BIO-TMP-0702 Revision: 00
	TITLE Statistical Analysis Plan	Effective date: 16-Mar-2018 Department: BIO

If non-inferiority is demonstrated in both the Per Protocol (PP) and Intention to Treat (ITT) populations, the trial will be declared a success. Because both analysis populations will be considered simultaneously, no adjustment for alpha is necessary.

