#### 4.1.3 Controlling for Multiplicity

The primary safety and efficacy endpoint will be evaluated simultaneously in the co-primary PP and ITT populations, and trial success requires meeting the non-inferiority criterion in both analyses. For the non-inferiority testing of the primary endpoint, adjustment for Type I error is not necessary.

The secondary powered endpoint hypothesis will only be tested if the primary endpoint non-inferiority hypothesis is met. Superiority for the primary endpoint will be formally tested if the secondary powered endpoint hypothesis is confirmed.

	FORM	Document No BIO-TMP-0702 Revision: 00
	TITLE Statistical Analysis Plan	Effective date: 16-Mar-2018 Department: BIO

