## 5.3 Secondary Endpoints

### 5.3.1 Secondary Powered Endpoint

The powered secondary endpoint of long-term safety and efficacy, defined as TLF between 12 months and 5 years by landmark Kaplan-Meier analysis, will be a test for superiority of the BuMA DES group to the DP EES group via the log-rank test in the ITT population. Subjects who experience TLF prior to 12 months will be excluded from this analysis. The analysis will be performed when the last enrolled subject has completed his/her 5-year clinical follow-up visit, and will be performed only if non-inferiority for the primary endpoint has been met.

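### The approximately 80% power quoted for the 12-month-to-5-year superiority endpoint is conditional on passing the non-inferiority gate; with the gate it is about 63-64% under the plan's own assumptions

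*SAP*

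**What the plan says.** SAP 4.1.2 lists the landmark assumptions: 2:1 allocation, 8% control TLF between 12 months and 5 years, 6.5% control TLF at 12 months, a constant hazard ratio of 0.52, 5% annual loss and two-sided alpha 0.05. It concludes that 1444 evaluable subjects at 1 year "will provide approximately 80% power to demonstrate superiority of the BuMA DES to DP EES using the log-rank test". Protocol 11.3.2 has the same text and the synopsis the same figure.

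The gate is stated elsewhere. SAP 4.1.3: "The secondary powered endpoint hypothesis will only be tested if the primary endpoint non-inferiority hypothesis is met". SAP 5.3.1 repeats that the analysis "will be performed only if non-inferiority for the primary endpoint has been met". SAP 4.1.3 also says that "trial success requires meeting the non-inferiority criterion in both analyses", meaning PP and ITT.

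The gate has its own power statement in SAP 4.1.1: "a sample size of 1551 evaluable subjects (1034 Intervention: 517 Control) will provide 80% power to demonstrate non-inferiority". It assumes no treatment difference (6.5% in both arms), a margin of 3.575% and one-sided alpha 0.025.

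**The concern.** The power sentence speaks of demonstrating superiority, and its list of assumptions does not include passing the gate. A reader of SAP 4.1.2 or Protocol 11.3.2 would conclude that a true hazard ratio of 0.52 would be shown four times in five. The design allows a formal claim only after a step that itself fails about one time in five under the plan's assumptions. If the two steps are close to independent, the chance of ending without the claim is about 36-37% rather than 20%. This is the trial's only powered long-term superiority endpoint, so the sponsor, the regulators and the ethics committees should know which probability is meant.

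**Working it through.** **1. The gate (SAP 4.1.1): the stated 80% reproduces.** Inputs: n_I = 1034, n_C = 517, p_I = p_C = 0.065, Δ = 0.03575, z = 1.960.

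Farrington-Manning power = Φ[(Δ − (p_I − p_C) − z·s0)/s1]. Here s0 uses the rates restricted to differ by Δ, and s1 the assumed rates.

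- Restricted rates: 0.0815 and 0.0458, so s0 = √(0.0815×0.9185/1034 + 0.0458×0.9542/517) = 0.01252.
- s1 = √(0.065×0.935×(1/1034 + 1/517)) = 0.01328.
- Power = Φ[(0.03575 − 1.960×0.01252)/0.01328] = Φ(0.844) = 80.1%.

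The smallest 2:1 total that reaches 80% is 1551, as the plan states.

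**2. The landmark test (SAP 4.1.2): the stated 80% reproduces if the test is certain to be run.** The sample size is 1632 × (1 − 0.05 − 0.065) = 1444.3. This removes 6.5% first-year TLF from the whole cohort, so it too assumes equal arms in year 1.

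- Control hazard: −ln(0.92)/4 = 0.02085 per year. Intervention: 0.52 × 0.02085 = 0.01084. Loss: −ln(0.95) = 0.05129.
- Probability of an observed event over 4 years = λ/(λ+μ) × [1 − exp(−4(λ+μ))]: 0.0384 for intervention, 0.0724 for control.
- Expected events: 962.7 × 0.0384 = 37.0 and 481.3 × 0.0724 = 34.9, together 71.8.

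| Method | Calculation | Power |
|---|---|---|
| Exponential, variance 1/e_I + 1/e_C | Φ(0.6539/0.2361 − 1.960) = Φ(0.810) | 79.1% |
| Freedman, 2:1 | Φ(√(2×71.8) × 0.48/2.04 − 1.960) = Φ(0.860) | 80.5% |
| Schoenfeld | Φ(0.6539 × √(71.8×2/9) − 1.960) = Φ(0.652) | 74.3% |

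Log-rank simulation gives 79-80%, in line with the first two methods.

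**3. Both steps together.** SAP 5.3.1 excludes subjects with TLF before 12 months, so the tests use events from disjoint periods and multiplying is a good approximation.

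- Exponential: 0.801 × 0.791 = 63.3%.
- Freedman: 0.801 × 0.805 = 64.5%.
- Nominal figures: 0.80 × 0.80 = 64%.
- Simulation of 1088:544 subjects through both tests, 10,000 runs, PP equal to ITT: gate 80.5%, landmark 79.8%, both 64.0%.
- The same simulation with a further 3% excluded from PP at random (illustrative; not in the documents): both-population gate 78.3%, all steps 61.5%.
- With Schoenfeld's more pessimistic landmark power the product is 0.801 × 0.743 = 59.5%.

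**4. Sensitivity to the first-year effect.** Control stays at 6.5%, intervention is 1 − 0.935^HR, and landmark power is held at 79.1%.

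| First-year HR | Intervention TLF | Gate power | Joint |
|---|---|---|---|
| 1.00 | 6.50% | 80.1% | 63.3% |
| 0.95 | 6.19% | 86.7% | 68.6% |
| 0.90 | 5.87% | 91.7% | 72.6% |
| 0.80 | 5.23% | 97.5% | 77.1% |
| 0.52 | 3.43% | 99.99% | 79.1% |

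**The case against.** A reader might infer that the 80% is an arithmetic error. It is not. It reproduces for a named test at a stated sample size, and giving power separately for each hypothesis is common in gated designs.

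The gate is not hidden either. SAP 4.1.3 directly follows the power statement under a shared heading, and in the synopsis the sentence just before the power paragraph states the gate. A careful reader could multiply the two figures. That stands, and it limits the point to one of labelling. It does not make the sentence complete, since nowhere is the 80% called conditional or a joint power given.

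The joint figure is also one scenario. SAP 4.1.2 lists a 12-month rate for control only and calls the hazard ratio constant. If 0.52 applied from randomization, the gate would be passed almost surely and overall power would stay near 79-80%. The documents do not support that as the planning assumption: SAP 4.1.1 states no first-year difference, and 1444 is obtained by removing 6.5% from both arms. The sensitivity is real, however, so the joint figure should always carry its assumption.

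A reader might also infer harm to the third step, the 12-month superiority test. In the scenario used here the arms are equal at 12 months, so reaching that test less often loses no power for a true effect.

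Finally, once the 12-month result is known, the conditional 80% is the relevant planning figure. That is a reason to label it, not to leave it unlabelled.

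**Conclusion.** The point holds as an omitted condition. The approximately 80% is the power of the landmark log-rank test given that it is performed. As gated, and under the plan's own assumptions, the design has about a 63-64% chance of demonstrating long-term superiority if PP and ITT coincide, and slightly less if they differ.

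This rests on 6.5% TLF in both arms at 12 months, a hazard ratio of 0.52 thereafter, an 8% control rate over the following 4 years, 5% annual loss, and near-independence of the two steps, which the simulation supports. Any true first-year benefit raises the figure towards 79-80%. Type I error control and the validity of the analyses are not in question.

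**What to change.** In SAP 4.1.2, Protocol 11.3.2 and the synopsis, replace the power statement with wording such as: *approximately 80% power conditional on the primary non-inferiority hypothesis being met; approximately 63-64% unconditionally, assuming 6.5% TLF in both arms at 12 months (about 73% if the first-year hazard ratio were 0.90, approaching 79-80% with a larger first-year benefit).*

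The cost is one sentence in each place and a less favourable headline figure. Sample size, alpha, testing order and analyses do not change.

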#### 4.1.3 Controlling for Multiplicity

The primary safety and efficacy endpoint will be evaluated simultaneously in the co-primary PP and ITT populations, and trial success requires meeting the non-inferiority criterion in both analyses. For the non-inferiority testing of the primary endpoint, adjustment for Type I error is not necessary.

The secondary powered endpoint hypothesis will only be tested if the primary endpoint non-inferiority hypothesis is met. Superiority for the primary endpoint will be formally tested if the secondary powered endpoint hypothesis is confirmed.

	FORM	Document No BIO-TMP-0702 Revision: 00
	TITLE Statistical Analysis Plan	Effective date: 16-Mar-2018 Department: BIO

#### 4.2 Interim Analyses and Summaries

No interim analyses for this study are planned.

#### 4.3 General Methods

All data collected will be summarized overall and by treatment. Descriptive statistics of continuous variables will include mean, standard deviation, median, quartiles, range, and sample size. Differences between the treatment arms, where specified, will be summarized with the differences of the two means, 95% confidence intervals for the difference between the means, and p-values based on a t-test. The distributions within each group will be tested for normality using the Shapiro-Wilks test and if normality cannot be assumed then a Wilcoxon rank-sum test for medians will be performed. The confidence interval for the difference of two means will be calculated under the assumption of unequal variances.

For categorical variables, descriptive statistics will include count, percentage, and sample size. Categorical data will be presented as n/N (%), and percentages will be rounded and reported to a single decimal point (xx.x %). Unless otherwise noted, subjects with missing data will be excluded from the denominator. Differences between the two treatment arms, where specified, will be summarized with the difference in percentages, the asymptotic 95% confidence interval for the difference of two percentages, and a p-value based on a chi-squared test. If 20% or more of the expected cell frequencies are less than 5 then a Fisher's Exact Test will be used to test for differences in proportions.

Survival analysis techniques will be used to analyze the time-to-event variables that occur at or after 30 days of follow-up. Time to event analysis will be performed for each time point separately (i.e. up to 30 days, 6-months (180 days), 1 year (365 days), 2 years (730 days), 3 years (1095 days), 4 years (1460 days), and 5 years (1825 days)) and summarized using the Kaplan-Meier estimated event rates and number of events. The log-rank test will be used for comparing treatments. Hazard ratios and the associated two sided confidence intervals (Wald's CI) will be estimated by Cox proportional hazards model, including treatment as a covariate.

All time-to-event analyses will be performed with time defined from date of randomization to first occurrence of an event. Subjects without events will be censored at their early withdrawal date or the last known event-free time point. If this event-free time point occurs after the analysis time point, the days to event variable will be set equal to the analysis time point so that the patient will be included in the analysis (e.g. if the last data point was collected at 1 year and 2 weeks post-procedure, for the 1-year analysis, this subject will be censored at exactly 1 year (365 days)). When analyzing composite endpoints, time is measured from randomization to the first event (days).

	FORM	Document No BIO-TMP-0702 Revision: 00
	TITLE Statistical Analysis Plan	Effective date: 16-Mar-2018 Department: BIO

Per protocol, patients may have multiple target lesions treated. For patient level endpoints, only one lesion per subject is required to meet the criteria for the endpoint. All clinical, procedural, and safety endpoints are summarized on a patient level, except when noted. All Angiographic Core Lab variables will be summarized on a lesion level.

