## **2.0 ENDPOINTS: DEFINITIONS AND CONVENTIONS**

### **2.1 Primary Endpoint**

The primary safety and efficacy endpoint of the study is target lesion failure (TLF) at 12 months. Target lesion failure (TLF) is defined as the composite of cardiac death, target vessel-related myocardial infarction (TV-MI), and clinically-driven target lesion revascularization (TLR).

All events will be adjudicated and classified by an independent Clinical Events Committee (CEC). Target-vessel myocardial infarction (TV-MI) events will be adjudicated per the modified Third Universal Definition. Details of the primary protocol definition of myocardial infarction are provided in Section 2.2.3.3.

	FORM TITLE Statistical Analysis Plan	Document Nº BIO-TMP-0702 Revision: 00 Effective date: 16-Mar-2018 Department: BIO
--	--	--

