#### **2.2.3.2 Mortality**

All death events will be adjudicated and classified by the CEC into the following categories (ARC-defined):

- **Cardiac:** Any death due to proximate cardiac cause (e.g., MI, low-output failure, fatal arrhythmia), unwitnessed death and death of unknown cause, and all procedure-related deaths, including those related to concomitant treatment, will be classified as cardiac death.
- **Vascular:** Death caused by non-coronary vascular causes, such as cerebrovascular disease, pulmonary embolism, ruptured aortic aneurysm, dissecting aneurysm, or other vascular diseases.
- **Non-cardiovascular:** Any death not covered by the above definitions, such as death caused by infection, malignancy, sepsis, pulmonary causes, accident, suicide, or trauma.

All death events will be reported and evaluated in-hospital and at 30 days, 6 months, and 1, 2, 3, 4, and 5 years, cumulatively and by individual categories.

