#### **4.4 Methods to Manage Missing Data**

Reasonable efforts will be made to obtain complete data for all patients; however, missing observations may occur. The reasons for missing data will be reported (e.g., patient is deceased, lost to follow up, withdrew consent, missed follow-up visit, etc.).

The primary endpoint analysis of TLF will be performed using all available data. As a sensitivity analysis, a tipping point analysis will be performed to assess the impact of missing values from subjects with insufficient 12 month follow-up. This analysis will include the worst-case scenario as the most extreme case.

All secondary endpoint analyses will be performed using all available data.

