### 5.3.2 Secondary Efficacy Endpoints

Lesion Success will be assessed on a lesion level, performed on the ITT analysis population, and presented for overall subjects and by treatment arm. The analysis of Device Success will include all

	FORM	Document No BIO-TMP-0702 Revision: 00
	TITLE Statistical Analysis Plan	Effective date: 16-Mar-2018 Department: BIO

target lesions in which the assigned device is attempted in the denominator [1]. As a secondary analysis, the device success analysis will include all target lesions in the denominator, whether or not an attempt to implant the assigned device was made.

No formal hypothesis testing will be performed. Both endpoints will be compared descriptively between the treatment arms using a generalized linear mixed model that accounts for the clustering effect of multiple lesions per subject. The model includes treatment as a fixed effect and subject as a random effect. Two sided 95% CI for the estimated difference and p-values will be reported.

Procedural success and in- hospital TVR, TLR, TVF, and TLF events will be evaluated in the ITT analysis population. No formal hypothesis testing will be performed. Descriptive statistics will include count, percentage, and sample size. Subjects with missing data will be excluded from the denominator. Differences between the two treatment arms will be summarized descriptively with the difference in percentages, the asymptotic 95% confidence interval for the difference of two percentages, and a p-value based on a chi-squared test. If 20% or more of the expected cell frequencies are less than 5 then a Fisher's Exact Test will be used to test for differences in proportions.

Survival analysis techniques, as detailed in Section 4.3, will be used to analyze the TVR, TLR, TVF, and TLF events at 30 days, 6 months, and 1, 2, 3, 4, and 5 years. Summary statistics will include Kaplan-Meier estimated event rates and number of events. The log-rank test will be used for comparing treatments. Hazard ratios and the associated two-sided confidence intervals (Wald's CI) will be estimated by Cox proportional hazards model, including treatment as a covariate.

A secondary analysis of all secondary efficacy endpoints will also be performed in the PP analysis population.

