### 5.3.3 Secondary Safety Endpoints

All secondary safety endpoints will be evaluated in the ITT analysis population. No formal hypothesis testing will be performed.

Descriptive statistics for in-hospital events will include count, percentage, and sample size. Subjects with missing data will be excluded from the denominator. Differences in event rates between the two treatment arms will be summarized descriptively with the difference in percentages, the asymptotic 95% confidence interval for the difference of two percentages, and a p-value based on a chi-squared test. If 20% or more of the expected cell frequencies are less than 5 then a Fisher's Exact Test will be used to test for differences in proportions.

	FORM	Document No: BIO-TMP-0702 Revision: 00
	TITLE Statistical Analysis Plan	Effective date: 16-Mar-2018 Department: BIO

Survival analysis techniques, as detailed in Section 4.3, will be used to analyze all secondary safety endpoints at 30 days, 6 months, and 1, 2, 3, 4, and 5 years. Summary statistics will include Kaplan-Meier estimated event rates and number of events. The log-rank test will be used for comparing treatments. Hazard ratios and the associated two-sided confidence intervals (Wald's CI) will be estimated by Cox proportional hazards model, including treatment as a covariate.

A secondary analysis of all secondary safety endpoints will also be performed in the PP analysis population.

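### Kaplan-Meier rates to 5 years censor deaths outside the endpoint, so they modestly overstate the proportion of subjects affected

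*SAP*

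**What the plan says.** SAP 4.3 analyses time-to-event endpoints at 30 days, 6 months and each year to 5 years, "summarized using the Kaplan-Meier estimated event rates and number of events". SAP 5.3.2 says that these methods "will be used to analyze the TVR, TLR, TVF, and TLF events at 30 days" and at the later time points. SAP 5.3.3 does the same for safety: "Survival analysis techniques, as detailed in Section 4.3, will be used to analyze all secondary safety endpoints". SAP 5.6.1 repeats the approach for site-reported events, and SAP 7.1 lists Kaplan-Meier figures for TLF, TVF, MACE and stent thrombosis. SAP 5.3.1 defines the powered secondary endpoint, TLF from 12 months to 5 years, through a landmark Kaplan-Meier analysis with a log-rank test.

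The censoring rule in SAP 4.3 is: "Subjects without events will be censored at their early withdrawal date or the last known event-free time point". It does not mention death. SAP 4.4 lists death with the other reasons for incomplete data: "The reasons for missing data will be reported (e.g., patient is deceased, lost to follow up, withdrew consent, missed follow-up visit, etc". Neither document mentions competing risks or cumulative incidence.

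TLF and TVF include cardiac death only. SAP 2.2.3.2 has two further classes of death that fall outside them: vascular death and non-cardiovascular death, the latter being "Any death not covered by the above definitions, such as death caused by infection, malignancy, sepsis, pulmonary causes, accident, suicide, or trauma".

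**The concern.** A subject who has died can no longer have a revascularization, an infarction or a bleed. Censoring at death treats that subject as still at risk, represented by those who remain. One minus Kaplan-Meier then estimates the event rate in a hypothetical population without the competing deaths. Readers will take it as the share of subjects who had the event.

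Which deaths compete depends on the endpoint:

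- TLF and TVF: non-cardiac deaths, that is, vascular and non-cardiovascular deaths.
- TLR and TVR: all deaths.
- MI, stent thrombosis and bleeding: any death that is not itself the event. Type 3 MI, unexplained death within 30 days (probable stent thrombosis) and BARC type 5 bleeding count as events.
- Cardiac and non-cardiac mortality reported separately: each competes with the other.

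At stake are the arm-level rates that will be quoted from the 2- to 5-year reports. The excess grows with follow-up. It is larger in the arm with more events, so it also slightly enlarges the absolute difference between arms if the planned hazard ratio holds.

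**Working it through.** **Inputs from the documents** (SAP 4.1.2; Protocol 11.3.2): control TLF 6.5% in year 1 and 8% between 12 months and 5 years; hazard ratio 0.52; 2:1 allocation; loss 5% per year; 1444 evaluable subjects at 1 year; about 80% power.

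**Assumption not in the documents:** competing death rate m of 1% to 3% per year, constant and equal in both arms.

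**Step 1: the plan's own figure.** With exponential hazards, the control hazard is -ln(0.92)/4 per year, the intervention hazard is 0.52 times that, and the loss hazard is -ln(0.95) per year. Expected events are 34.9 control + 37.0 intervention, or 71.8 before rounding. Freedman's formula for 2:1 allocation needs 70.9 events and gives 80.5% power. A simulated log-rank test (20,000 runs) gives 78.8%. Schoenfeld's formula is lower, at 74.3%. The stated power of approximately 80% is reproduced by the first two. The 1444 is close to 1632 × 0.95 × 0.935 = 1450.

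**Step 2: the two estimators.** For event hazard l, competing hazard m and time T:

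- 1 - KM = 1 - exp(-lT)
- cumulative incidence = l/(l+m) × [1 - exp(-(l+m)T)]

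For 5-year TLF the hazard is l1 = -ln(0.935) = 0.0672 in year 1 and l2 = -ln(0.92)/4 = 0.0208 per year afterwards:

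- 1 - KM = 1 - 0.935 × 0.92 = 13.98%
- cumulative incidence = CI(l1, m, 1) + exp(-(l1+m)) × CI(l2, m, 4)

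At m = 2%, this is 0.0644 + 0.9165 × 0.0769 = 0.1349.

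| Quantity | KM | m = 1% | m = 2% | m = 3% | Excess of KM (points) |
|---|---|---|---|---|---|
| 1-year TLF, control | 6.50% | 6.47% | 6.44% | 6.40% | 0.03 to 0.10 |
| 5-year TLF, control | 13.98% | 13.73% | 13.49% | 13.25% | 0.25 to 0.73 |
| Landmark TLF, control | 8.00% | 7.84% | 7.69% | 7.54% | 0.16 to 0.46 |
| Landmark TLF, intervention | 4.24% | 4.16% | 4.08% | 4.00% | 0.08 to 0.24 |
| Landmark difference | 3.76 | 3.68 | 3.61 | 3.54 | 0.08 to 0.22 |

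As a share of the Kaplan-Meier rate, the 5-year TLF excess is 0.25/13.98 = 1.8% to 0.73/13.98 = 5.2%. If every first-year event fell on day 0, the excess would be 0.22 to 0.63 points.

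The documents give no 5-year rates for the single endpoints. For illustration, with a constant hazard and m from 1% to 3%, a Kaplan-Meier rate of 1% corresponds to 0.98% to 0.93% affected, 5% to 4.88% to 4.65%, and 10% to 9.76% to 9.30%.

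**Step 3: check by simulation.** With 400,000 control subjects, the landmark hazard, 5% annual loss and m = 2%, Kaplan-Meier gives 8.01%, Aalen-Johansen 7.70%, and the true proportion affected is 7.71%.

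**Step 4: the tests.** With m = 2% in both arms and no treatment effect, the simulated log-rank test rejects in 5.0% of runs. Power falls from 78.8% to 78.0% (m = 1%) and 77.4% (m = 2%). That loss comes from the deaths removing events and does not depend on the estimator used for the rates.

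**The case against.** The strongest reply is that nothing inferential depends on this. SAP 5.3.2 and 5.3.3 disclaim formal testing, the rates are openly labelled Kaplan-Meier, and deaths are reported by category at every time point. The excess is also well inside sampling error: with 544 controls at 14%, the 95% half-width is 1.96 × √(0.14 × 0.86/544) = 2.9 points, ignoring loss. All of this stands and limits the weight of the point. It does not remove a bias that always runs in one direction and is cheap to avoid.

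The TLF excess may lie towards the low end. Protocol Appendix A counts deaths as cardiac unless an unequivocal other cause is established, so doubtful deaths become TLF events. Protocol 6.2.2.1 excludes subjects with known illness giving a life expectancy under 1 year, severe renal insufficiency or LVEF below 30%. The age limit of 99 is only a cap and says nothing about the age distribution. Censoring at death is also inferred from SAP 4.3, not stated there.

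Three stronger readings are tempting but not supported:

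- A reader might infer that the primary result is biased. SAP 5.2.1 analyses 12-month TLF as a proportion by Farrington-Manning, not by Kaplan-Meier.
- A reader might spread 14% evenly over 5 years and obtain an excess of 0.3 to 1.0 points. The plan puts 6.5% in year 1, before much competing mortality has accrued, which lowers the range to 0.25 to 0.73.
- A reader might object that the rates will disagree with crude percentages beside them. From 30 days on, the SAP specifies event counts beside the Kaplan-Meier rate. With 5% annual loss, cumulative incidence would not equal a crude percentage either.

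**Conclusion.** The point holds as a modest reporting bias. As the SAP reads, deaths outside the endpoint are censored, and the rates for TLF, TVF, TLR, TVR, MI, stent thrombosis and bleeding overstate the proportion affected, increasingly so at later years. For TLF the size is a fraction of a point at the planning rates. This rests on competing death of 1% to 3% per year, which the documents do not supply, on piecewise constant hazards, and on equal competing mortality in both arms.

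The log-rank and Cox analyses remain valid as cause-specific comparisons. MACE and all-cause mortality are unaffected because every death is an event. In-hospital rates are simple proportions and are also unaffected. This is a worthwhile improvement, not a threat to the trial's conclusions.

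**What to change.** In SAP 4.3, state explicitly how a death outside the endpoint is handled. In SAP 4.3, 5.3.2, 5.3.3 and 5.6.1, for the descriptive landmark rates in 5.3.1, and in the TLF, TVF and stent thrombosis figures listed in 7.1, report Aalen-Johansen cumulative incidence with deaths outside the endpoint as the competing event. For cardiac and non-cardiac mortality, let each compete with the other. List the deaths that count as events for MI, stent thrombosis and bleeding.

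Show the Kaplan-Meier rates alongside. Keep the log-rank test, including the one for the powered secondary endpoint, and the Cox model, and label both as cause-specific. Leave MACE and all-cause mortality as they are.

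The cost is small: a different estimator on data already collected, since the CEC classifies every death (SAP 2.2.3.2). The downside is that the new rates will be slightly lower than the Kaplan-Meier figures in earlier stent trials, which is the reason to show both.
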